12.9 Reimbursement, Indemnity, and Insurance

Reimbursement, indemnity, and insurance are addressed in separate documentation.

12.10 Adherence to the Protocol

Except for a change that is intended to eliminate an immediate hazard to subjects, the approved protocol shall be conducted as described. All protocol deviations must be documented. Any protocol-related issues that pose an immediate or significant hazard to subjects must be reported to [REDACTED] on behalf of Gage Development Company, LLC immediately.

13 INVESTIGATOR OBLIGATIONS

Clinical research studies are subject to the regulations of the FDA. Prior to beginning the study, the investigator will be asked to demonstrate compliance with ICH E6, 8.2 and 21 CFR 312 by providing [REDACTED] with the signed essential documents required for the clinical trial. The responsibilities imposed upon investigators by the FDA are summarized in the “Statement of Investigator Form” (Form FDA-1572) which documents that he or she will follow the FDA regulations with respect to this study.

The investigator agrees to assume the responsibilities stated on the Form FDA-1572, and signifies his or her agreement by signing the Form FDA-1572, these responsibilities include:

- To conduct the study in accordance with the Study Protocol, Reference Drug Label, GCPs, International Conference on Harmonisation (ICH), and Declaration of Helsinki.
- To secure prior approval of the study by an appropriate IRB. This board should be constituted in conformity with FDA regulations.
- To report on the progress of the study to the IRB and to submit a final report within three months of the conclusion of data collection.
- To maintain current records of the receipt, dispensing, and disposition of study product and to return all unused product to the sponsor or the sponsor’s designated agent.
- To obtain a valid, fully informed, freely given written consent from each subject who participates in the study.
- To maintain adequate study documentation, including hospital records, laboratory results and lab records, and to store these case histories for a minimum of two years following notification by the sponsor that all investigations have been discontinued or that the FDA has approved the drug application.
- To identify all sub-investigators who will also supervise drug administration.
- To report all AEs to the sponsor or designated agent promptly.
- To allow inspection or copying by the FDA, sponsor, or sponsor’s designated agent of case histories and records of drug distribution.

Investigator Documentation required:

Prior to beginning the study, the investigator will be asked to comply with ICH E6, 8.2 and 21 CFR 312 by providing the following essential documents, including but not limited to:

1. A signed Protocol Signature Page.
2. A signed acknowledgement of receipt of the US Prescribing Information for the reference drug.
3. An IRB-approved Informed Consent.
4. IRB approval of protocol and ICF.
5. Form FDA 1572, fully executed, and all updates on a new fully executed Form FDA 1572.

6. Current Curriculum Vitae (CV) for the principal investigator and each sub-investigator listed on Form FDA 1572.
7. Medical license for principal investigator
8. A signed declaration of any financial conflict of interest (i.e., Financial Disclosure Form, financial disclosure).

Metronidazole Vaginal Gel is the intravaginal dosage form of the synthetic antibacterial agent, metronidazole, USP at a concentration of 0.75%. Metronidazole is a member of the imidazole class of antibacterial agents and is classified therapeutically as an antiprotozoal and antibacterial agent. Chemically, metronidazole is a 2-methyl-5-nitroimidazole-1-ethanol. It has a chemical formula of C₆H₉N₃O₃, a molecular weight of 171.16, and has the following structure:

Metronidazole Vaginal Gel is a gelled, purified water solution, containing metronidazole at a concentration of 7.5 mg/g (0.75%). The gel is formulated at pH 4.0. The gel also contains carbomer 934P, edetate disodium, methylparaben, propylparaben, propylene glycol, and sodium hydroxide.

Each applicator full of 5 grams of vaginal gel contains approximately 37.5 mg of metronidazole.

CLINICAL PHARMACOLOGY**Normal Subjects:**

Following a single, intravaginal 5 gram dose of metronidazole vaginal gel (equivalent to 37.5 mg of metronidazole) to 12 normal subjects, a mean maximum serum metronidazole concentration of 237 ng/mL was reported (range: 152 to 368 ng/mL). This is approximately 2% of the mean maximum serum metronidazole concentration reported in the same subjects administered a single, oral 500 mg dose of metronidazole (mean C = 12,785 ng/mL, range: 10,013 to 17,400 ng/mL). These peak concentrations were obtained in 6 to 12 hours after dosing with metronidazole vaginal gel and 1 to 3 hours after dosing with oral metronidazole.

The extent of exposure [area under the curve (AUC)] of metronidazole, when administered as a single intravaginal 5 gram dose of metronidazole vaginal gel (equivalent to 37.5 mg of metronidazole), was approximately 4% of the AUC of a single oral 500 mg dose of metronidazole (4977 ng·hr/mL and approximately 125,000 ng·hr/mL, respectively).

Dose-adjusted comparisons of AUCs demonstrated that, on a mg to mg comparison basis, the absorption of metronidazole, when administered vaginally, was approximately half that of an equivalent oral dosage.

Patients with Bacterial Vaginosis:

Following single and multiple 5 gram doses of metronidazole vaginal gel to 4 patients with bacterial vaginosis, a mean maximum serum metronidazole concentration of 214 ng/mL on day 1 and 294 ng/mL (range: 228 to 349 ng/mL) on day five were reported. Steady state metronidazole serum concentrations following oral dosages of 400 to 500 mg BID have been reported to range from 6,000 to 20,000 ng/mL.

Microbiology:

The intracellular targets of action of metronidazole on anaerobes are largely unknown. The 5-nitro group of metronidazole is reduced by metabolically active anaerobes, and studies have demonstrated that the reduced form of the drug interacts with bacterial DNA. However, it is not clear whether interaction with DNA alone is an important component in the bactericidal action of metronidazole on anaerobic organisms.

Culture and sensitivity testing of bacteria are not routinely performed to establish the diagnosis of bacterial vaginosis. (See **INDICATIONS AND USAGE**.)

Standard methodology for the susceptibility testing of the potential bacterial vaginosis pathogens, *Gardnerella vaginalis*, *Mobiluncus* spp., and *Mycoplasma hominis*, has not been defined. Nonetheless, metronidazole is an antimicrobial agent active in vitro against most strains of the following organisms that have been reported to be associated with bacterial vaginosis:

Bacteroides spp.

Gardnerella vaginalis

Mobiluncus spp.

Peptostreptococcus spp.

INDICATIONS AND USAGE

Metronidazole Vaginal Gel is indicated in the treatment of bacterial vaginosis (formerly referred to as *Haemophilus* vaginitis, *Gardnerella* vaginitis, nonspecific vaginitis, *Corynebacterium* vaginitis, or anaerobic vaginosis).

NOTE: For purposes of this indication, a clinical diagnosis of bacterial vaginosis is usually defined by the presence of a homogeneous vaginal discharge that (a) has a pH of greater than 4.5, (b) emits a “fishy” amine odor when mixed with a 10% KOH solution, and (c) contains clue cells on microscopic examination. Gram’s stain results consistent with a diagnosis of bacterial vaginosis include (a) markedly reduced or absent *Lactobacillus* morphology, (b) predominance of *Gardnerella* morphotype, and (c) absent or few white blood cells.

Other pathogens commonly associated with vulvovaginitis, e.g., *Trichomonas vaginalis*, *Chlamydia trachomatis*, *N. gonorrhoeae*, *Candida albicans*, and *Herpes simplex* virus should be ruled out.

CONTRAINdications

Metronidazole Vaginal Gel is contraindicated in patients with a prior history of hypersensitivity to metronidazole, parabens, other ingredients of the formulation, or other nitroimidazole derivatives.

WARNINGS

Convulsive Seizures and Peripheral Neuropathy:

Convulsive seizures and peripheral neuropathy, the latter characterized mainly by numbness or paresthesia of an extremity, have been reported in patients treated with oral or intravenous metronidazole. The appearance of abnormal neurologic signs demands the prompt discontinuation of metronidazole vaginal gel therapy. Metronidazole vaginal gel should be administered with caution to patients with nervous system diseases.

Psychotic Reactions:

Psychotic reactions have been reported in alcoholic patients who were using oral metronidazole and disulfiram concurrently. Metronidazole vaginal gel should not be administered to patients who have taken disulfiram within the last two weeks.

PRECAUTIONS

Metronidazole Vaginal Gel affords minimal peak serum levels and systemic exposure (AUCs) of metronidazole compared to 500 mg oral metronidazole dosing. Although these lower levels of exposure are less likely to produce the common reactions seen with oral metronidazole, the possibility of these and other reactions cannot be excluded presently. Data from well-controlled trials directly comparing metronidazole administered orally to metronidazole administered vaginally are not available.

General:

Patients with severe hepatic disease metabolize metronidazole slowly. This results in the accumulation of metronidazole and its metabolites in the plasma. Accordingly, for such patients, metronidazole vaginal gel should be administered cautiously.

Known or previously unrecognized vaginal candidiasis may present more prominent symptoms during therapy with metronidazole vaginal gel. Approximately 6-10% of patients treated with Metronidazole Vaginal Gel developed symptomatic *Candida* vaginitis during or immediately after therapy.

Disulfiram-like reaction to alcohol has been reported with oral metronidazole, thus the possibility of such a reaction occurring while on metronidazole vaginal gel therapy cannot be excluded.

Metronidazole Vaginal Gel contains ingredients that may cause burning and irritation of the eye. In the event of accidental contact with the eye, rinse the eye with copious amounts of cool tap water.

Information for the Patient:

The patient should be cautioned about drinking alcohol while being treated with metronidazole vaginal gel. While blood levels are significantly lower with Metronidazole Vaginal Gel than with usual doses of oral metronidazole, a possible interaction with alcohol cannot be excluded.

The patient should be instructed not to engage in vaginal intercourse during treatment with this product.

Drug Interactions:

Oral metronidazole has been reported to potentiate the anticoagulant effect of warfarin and other coumarin anticoagulants, resulting in a prolongation of prothrombin time. This possible drug interaction should be considered when metronidazole vaginal gel is prescribed for patients on this type of anticoagulant therapy.

In patients stabilized on relatively high doses of lithium, short-term oral metronidazole therapy has been associated with elevation of serum lithium levels and, in a few cases, signs of lithium toxicity.

Use of cimetidine with oral metronidazole may prolong the half-life and decrease plasma clearance of metronidazole.

Drug/Laboratory Test Interactions:

Metronidazole may interfere with certain types of determinations of serum chemistry values, such as aspartate aminotransferase (AST, SGOT), alanine aminotransferase (ALT, SGPT), lactate dehydrogenase (LDH), triglycerides, and glucose hexokinase. Values of zero may be observed. All of the assays in which interference has been reported involve enzymatic coupling of the assay to oxidation-reduction of nicotinamide-adenine dinucleotides (NAD + NADH). Interference is due to the similarity in absorbance peaks of NADH (340 nm) and metronidazole (322 nm) at pH 7.

Carcinogenesis, Mutagenesis, Impairment of Fertility:

Metronidazole has shown evidence of carcinogenic activity in a number of studies involving chronic oral administration in mice and rats. Prominent among the effects in the mouse was the promotion of pulmonary tumorigenesis. This has been observed in all six reported studies in that species, including one study in which the animals were dosed on an intermittent schedule (administration during every fourth week only). At very high dose levels (approximately 500 mg/kg/day), there was a statistically significant increase in the incidence of malignant liver tumors in males. Also, the published results of one of the mouse studies indicate an increase in the incidence of malignant lymphomas as well as pulmonary neoplasms associated with lifetime feeding of the drug. All these effects are statistically significant. Several long-term oral dosing studies in the rat have been completed. There were statistically significant increases in the

incidence of various neoplasms, particularly in mammary and hepatic tumors, among female rats administered metronidazole over those noted in the concurrent female control groups. Two lifetime tumorigenicity studies in hamsters have been performed and reported to be negative. These studies have not been conducted with 0.75% metronidazole vaginal gel, which would result in significantly lower systemic blood levels than those obtained with oral formulations.

Although metronidazole has shown mutagenic activity in a number of in vitro assay systems, studies in mammals (in vivo) have failed to demonstrate a potential for genetic damage.

Fertility studies have been performed in mice up to six times the recommended human oral dose (based on mg/m²) and have revealed no evidence of impaired fertility.

Pregnancy: Teratogenic Effects:

Pregnancy Category B

There has been no experience to date with the use of Metronidazole Vaginal Gel in pregnant patients. Metronidazole crosses the placental barrier and enters the fetal circulation rapidly. No fetotoxicity or teratogenicity was observed when metronidazole was administered orally to pregnant mice at six times the recommended human dose (based on mg/m²); however, in a single small study where the drug was administered intraperitoneally, some intrauterine deaths were observed. The relationship of these findings to the drug is unknown.

There are, however, no adequate and well-controlled studies in pregnant women. Because animal reproduction studies are not always predictive of human response, and because metronidazole is a carcinogen in rodents, this drug should be used during pregnancy only if clearly needed.

Nursing Mothers:

Specific studies of metronidazole levels in human milk following intravaginally administered metronidazole have not been performed. However, metronidazole is secreted in human milk in concentrations similar to those found in plasma following oral administration of metronidazole.

Because of the potential for tumorigenicity shown for metronidazole in mouse and rat studies, a decision should be made whether to discontinue nursing or to discontinue the drug, taking into account the importance of the drug to the mother.

Pediatric Use:

Safety and effectiveness in children have not been established.

ADVERSE EVENTS

Clinical Trials:

There were no deaths or serious adverse events related to drug therapy in clinical trials involving 800 non-pregnant women who received Metronidazole Vaginal Gel.

In a randomized, single-blind clinical trial of 505 non-pregnant women who received Metronidazole Vaginal Gel once or twice a day, 2 patients (one from each regimen) discontinued therapy early due to drug-related adverse events. One patient discontinued drug because of moderate abdominal cramping and loose stools, while the other patient discontinued drug because of mild vaginal burning. These symptoms resolved after discontinuation of drug.

Medical events judged to be related, probably related, or possibly related to administration of Metronidazole Vaginal Gel once or twice a day were reported for 195/505 (39%) patients. The incidence of individual adverse reactions were not significantly different between the two regimens. Unless percentages are otherwise stipulated, the incidence of individual adverse reactions listed below was less than 1%:

Reproductive:

Vaginal discharge (12%),
Symptomatic *Candida* cervicitis/vaginitis (10%),
Vulva/vaginal irritative symptoms (9%),
Pelvic discomfort (3%).

Gastrointestinal:

Gastrointestinal discomfort (7%),
Nausea and/or vomiting (4%),
Unusual taste (2%),
Diarrhea/loose stools (1%),
Decreased appetite (1%),
Abdominal bloating/gas; thirsty, dry mouth.

Neurologic:

Headache (5%), Dizziness (2%), Depression.

Dermatologic:

Generalized itching or rash.

Other:

Unspecified cramping (1%),

Fatigue,

Darkened urine.

In previous clinical trials submitted for approved labeling of Metronidazole Vaginal Gel the following was also reported:

Laboratory:

Increased/decreased white blood cell counts (1.7%).

Other Metronidazole Formulations:

Other effects that have been reported in association with the use of topical (dermal) formulations of metronidazole include skin irritation, transient skin erythema, and mild skin dryness and burning. None of these adverse events exceeded an incidence of 2% of patients.

Metronidazole Vaginal Gel affords minimal peak serum levels and systemic exposure (AUC) of metronidazole compared to 500 mg oral metronidazole dosing. Although these lower levels of exposure are less likely to produce the common reactions seen with oral metronidazole, the possibility of these and other reactions cannot be excluded presently.

The following adverse reactions and altered laboratory tests have been reported with the **oral or parenteral** use of metronidazole:

Cardiovascular: Flattening of the T-wave may be seen in electrocardiographic tracings.

Central Nervous System: (See **WARNINGS.**) Headache, dizziness, syncope, ataxia, confusion, convulsive seizures, peripheral neuropathy, vertigo, incoordination, irritability, depression, weakness, insomnia.

Gastrointestinal: Abdominal discomfort, nausea, vomiting, diarrhea, an unpleasant metallic taste, anorexia, epigastric distress, abdominal cramping, constipation, “furry” tongue, glossitis, stomatitis, pancreatitis, and modification of taste of alcoholic beverages.

Genitourinary: Overgrowth of Candida in the vagina, dyspareunia, decreased libido, proctitis.

Hematopoietic: Reversible neutropenia, reversible thrombocytopenia.

Hypersensitivity Reactions: Urticaria; erythematous rash; flushing; nasal congestion; dryness of the mouth, vagina, or vulva; fever; pruritus; fleeting joint pains.

Renal: Dysuria, cystitis, polyuria, incontinence, a sense of pelvic pressure, darkened urine.

OVERDOSAGE

There is no human experience with overdosage of metronidazole vaginal gel. Vaginally applied metronidazole gel, 0.75% could be absorbed in sufficient amounts to produce systemic effects. (See **WARNINGS.**)

DOSAGE AND ADMINISTRATION

The recommended dose is one applicator full of Metronidazole Vaginal Gel (approximately 5 grams containing approximately 37.5 mg of metronidazole) intravaginally once or twice a day for 5 days. For once-a-day dosing, Metronidazole Vaginal Gel should be administered at bedtime.

HOW SUPPLIED

Metronidazole Vaginal Gel 0.75% is supplied in a 70 gram tube and packaged with 5 vaginal applicators.

The NDC number for the 70 gram tube is 68682-455-70.

Store at controlled room temperature 15° to 30°C (59° to 86°F). Protect from freezing.

Clinical Studies

In a randomized, single-blind clinical trial of non-pregnant women with bacterial vaginosis who received Metronidazole Vaginal Gel daily for 5 days, the clinical cure rates for evaluable patients determined at 4 weeks after completion of therapy for the QD and BID regimens were 98/185 (53%) and 109/190 (57%), respectively.

Rx Only

[figure not shown]
[figure not shown]
[figure not shown]
Manufactured for: Valeant Pharmaceuticals North America LLC, Bridgewater, NJ 08807

By: DPT Laboratories, Inc., San Antonio, TX 78215

Rev. 11/14

DIRECTIONS FOR USE**1. Filling the applicator**

- Remove cap and puncture metal seal on tube with the pointed tip of cap. (See Figure 1)
- Screw end of applicator onto tube. (See Figure 2)
- Slowly squeeze gel out of tube and into applicator. Plunger will stop when the applicator is full. (See Figure 3)
- Unscrew applicator and replace cap on tube.

**Figure 1****Figure 2****Figure 3**

2. Inserting the applicator

- The applicator may be inserted while lying on your back with your knees bent or in any comfortable position
- Hold filled applicator by barrel, and gently insert into vagina as far as it will comfortably go. (See Figure 4)
- Slowly press the plunger until it stops to deposit gel into vagina and then withdraw the applicator.

[figure not shown]

Figure 4

3. Care of the applicator

If physician prescribes twice-a-day dosing:

- After use, pull the plunger out of the barrel. (See Figure 5)
- Wash both plunger and barrel in warm soapy water and rinse thoroughly.
- To reassemble applicator, gently push plunger back into barrel.

[figure not shown]

Figure 5

IMPORTANT:

For once-a-day dosing, apply one applicator full at bedtime. For twice-a-day dosing, apply one applicator full each morning and evening for five days, or as directed by physician.

WARNINGS:

- If significant irritation develops from the use of this medication, discontinue use and consult your physician.
- Do not use during pregnancy except under the supervision of a physician.
- Keep this and all medications out of reach of children.
- For vaginal use only. Not for use in the eyes, on the skin or in the mouth.

Store at room temperature. Avoid exposure to extreme heat or cold.

See end of carton and bottom of tube for lot number and expiration date.

Manufactured for: Valeant Pharmaceuticals North America LLC, Bridgewater, NJ 08807

By: DPT Laboratories, Inc., San Antonio, TX 78215

Rev. 11/14

9432501

140410-1114

PACKAGE LABEL.PRINCIPAL DISPLAY PANEL - 70 gram Carton

NDC 68682-455-70

Rx Only

Metronidazole Vaginal Gel, 0.75%

with 5 applicators

FOR INTRAVAGINAL USE ONLY. (NOT FOR OPHTHALMIC, DERMAL, OR ORAL USE.)

Net Wt. 70 g

OCEANSIDE PHARMACEUTICALS®

METRONIDAZOLE

metronidazole gel

Product Information

Product Type	HUMAN PRESCRIPTION DRUG	Item Code (Source)	NDC:68682-455
Route of Administration	VAGINAL		

Active Ingredient/Active Moiety

Ingredient Name	Basis of Strength	Strength
METRONIDAZOLE (UNII: 140 QMO216 E) (METRONIDAZOLE - UNII:140 QMO216 E)	METRONIDAZOLE	7.5 mg in 1 g

Inactive Ingredients

Ingredient Name	Strength
CARBOMER 934 (UNII: Z135WT9208)	
EDETA TE DISODIUM (UNII: 7FLD91C86K)	
METHYLPARABEN (UNII: A2I8C7HI9T)	
PROPYLPARABEN (UNII: Z8IX2SC1OH)	
PROPYLENE GLYCOL (UNII: 6DC9Q167V3)	
SODIUM HYDROXIDE (UNII: 55X04QC32I)	

Packaging

#	Item Code	Package Description	Marketing Start Date	Marketing End Date
1	NDC:68682-455-70	70 g in 1 TUBE, WITH APPLICATOR		

Marketing Information

Marketing Category	Application Number or Monograph Citation	Marketing Start Date	Marketing End Date
NDA AUTHORIZED GENERIC	NDA020208	04/01/2015	

Labeler - Oceanside Pharmaceuticals (832011691)**Establishment**

Name	Address	ID/FEI	Business Operations
DPT Laboratories, Ltd.		832224526	MANUFACTURE (68682-455)

Revised: 4/2015

Oceanside Pharmaceuticals

Appendix 2 SUBJECT DOSING INSTRUCTIONS FOR STUDY MEDICATION**SUBJECT DOSING INSTRUCTIONS FOR STUDY MEDICATION**
Bacterial Vaginosis Study
Protocol GDC-229-002

Please follow these instructions exactly as they are written below. Contact the study staff at the telephone number below if you have any questions about the study.

Name: _____ Phone: _____

Your study medication kit includes a 70 gram tube of study medicine and 5 vaginal applicators. The study medicine is to be applied into the vagina using a new applicator each night at bedtime for five consecutive nights. You will start on the same day that you were given this medication by the study site.

NOTE: It is important for you to continue to use the study medication during the prescribed 5-day treatment period unless directed to do otherwise by the study doctor. Do not discontinue the use of the medication unless directed so by the study staff. Talk to the study staff about any side effects that you experience.

- You should not drink alcohol on Days 1 to 6 (during the five days of treatment and for one day afterward).
- You should not engage in sexual intercourse
 - on Days 1 to 7 (during five days of treatment and for two days afterward) or
 - 48 hours before Visit 2 and Visit 3.
- **Do not use any intravaginal product other than study medication for the duration of this trial.** This includes: spermicide, tampon, douche, feminine deodorant spray, diaphragm, vaginal ring birth control, or condom with spermicide.
- Do not insert into the vagina any drug (e.g. Monistat, etc.), or non-drug product during this study; also do not use any topical vaginal products (e.g., hydrocortisone, etc.) for the duration of this trial.
- If you miss a dose, take the next dose at the usual time the following evening. Report any missed doses to the study staff at your next visit.
- It is recommended to empty bladder completely prior to administering study drug.
- If significant irritation develops from the use of this medication consult the study doctor.
- Keep this and all medications out of reach of children.
- Do not allow anyone else to use this study medication.
- For vaginal use only. Not for use in the eyes, on the skin or in the mouth.
- Store the study medication at room temperature.

Study Visit Schedule:

Visit	Calendar Day	Date	Time
2			
3			

Bring this instruction sheet, unused study medication, and any unused applicators to each study visit.

Step 1 Fill the applicator

- a) You have been given five (5) applicators -- one for each night that you will need to use the study medication.
- b) Remove the cap from the tube of study medication and puncture the metal seal on the top of the tube with the pointed tip of the cap. (See Figure 1)
- c) Screw the end of one applicator completely onto the tube. (See Figure 2)
- d) Slowly squeeze the gel out of the tube and into the applicator until the plunger stops moving (the plunger will stop when the applicator is full). (See Figure 3)
- e) Unscrew the applicator and replace the cap onto the tube.

[figure not shown]

Figure 1

[figure not shown]

Figure 2

[figure not shown]

Figure 3

Step 2 Insert the applicator

- a) The applicator may be inserted while lying on your back with your knees bent or in any comfortable position.
- b) Hold the filled applicator by the applicator barrel and gently insert it into your vagina as far as it will comfortably go. (See Figure 4)
- c) Slowly press the plunger until it stops in order to insert all of the gel into your vagina and then withdraw the applicator.
- d) Throw away the used applicator. Do not reuse it.

Figure 4

Step 3 Return Instructions

- a) Return the tube of remaining study medication with all original packaging to the study site at your next visit.
- b) Return all **unused** applicators to the study site at your next visit.

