- Dispense study medication, explain appropriate application to subjects, and give the subject a copy of the Subject Dosing Instructions for Study Medication ([Appendix 2](#)).
- Schedule the subject for Visit 2 and Visit 3 and add the visit dates to page 2 of the Subject Dosing Instructions for Study Medication. Note: The subject should not be menstruating during the five days of study medication administration or be scheduled for Study Visits 2 or 3 when menstruating in order for assessments to be accurate.

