5.5 Unscheduled Visit

The investigator may see the subject for an unscheduled visit to manage or assess AEs.

At this visit, the investigator or designee will:

- Assess AEs and local site reactions since the last visit; AEs and local site reactions will be recorded.
- Record any changes in the subject's concomitant medications.
- Confirm the next appointment (to be done at a time the subject does not expect to be menstruating).

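### For significant irritation, the subject dosing sheet drops the label's instruction to stop use, turning stop-then-call into call-then-stop without a stated reason (minor safety wording)

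*Protocol*

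**What the plan says.** Protocol Appendix 1 reproduces the reference product's prescribing information. The warnings at the end of its Directions for Use tell the patient: "If significant irritation develops from the use of this medication, discontinue use and consult your physician".

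Protocol Appendix 2 is the subject's own instruction sheet. Its corresponding bullet reads: "If significant irritation develops from the use of this medication consult the study doctor". A note higher on the same sheet asks subjects to complete the five days unless the study doctor directs otherwise, and adds: "Do not discontinue the use of the medication unless directed so by the study staff". The note makes no exception for irritation.

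Appendix 2 is the document subjects actually take home. Protocol 5.1 tells the site to "give the subject a copy of the Subject Dosing Instructions for Study Medication". Protocol 13 has investigators agree "To conduct the study in accordance with the Study Protocol, Reference Drug Label, GCPs".

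The sheet also carries contact routes. It gives a telephone line ("Contact the study staff at the telephone number below if you have any questions about the study"), prompts subjects to raise side effects with staff, and refers irritation to the study doctor. It tolerates an omitted dose: "If you miss a dose, take the next dose at the usual time the following evening". Elsewhere, Protocol 5.5 provides that "The investigator may see the subject for an unscheduled visit to manage or assess AEs", and Protocol 3.4 lets a subject withdraw at any time.

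**The concern.** The irritation sentence was carried over from the label almost unchanged, except that the physician became the study doctor and the stop instruction disappeared. Together with the rule against stopping without staff direction, the sheet reads as an instruction to keep dosing until someone has been reached. The label lets the woman stop first.

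Protocol 3.5.3, which restates the label's warnings and precautions, neither repeats this patient direction nor explains the change. The protocol can mark a departure from the label when it means to: Protocol 3.5.3.3.1.1 identifies its longer abstinence rule on intercourse as a protocol addition. Nothing comparable appears here.

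What is at stake is subject comfort and safety over at most a few nightly doses. All three arms receive the same sheet, so the comparison between arms is not at issue.

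**Working it through.** **Texts side by side**

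| Situation | Label (Appendix 1) | Subject sheet (Appendix 2) |
|---|---|---|
| Significant irritation | Stop use, and consult physician | Consult study doctor |
| Stopping on own initiative | Directed, for significant irritation | Not unless staff direct it |
| Order of action | Stop, then call | Call, then stop if told to |

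Dosing is once nightly for five nights, so each day of delay in reaching staff costs about one further dose.

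**How many women**

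The documents give no rate for significant irritation. The nearest figure is in Protocol 3.5.3.4.1: of 505 women on once- or twice-daily gel, one stopped for vaginal burning (rated mild).

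- Rate 1/505 = 0.198%; exact (Clopper-Pearson) 95% interval 0.0050% to 1.098%.
- Two active arms, 2 × 246 = 492: 492/505 = 0.97 women (0.02 to 5.4).
- All 738 who receive the sheet: 738/505 = 1.46 (0.04 to 8.1), assuming the vehicle arm has the same rate.
- Upper context: the label's 9% for vulvar or vaginal irritative symptoms carries no severity limit. 0.09 × 492 = 44; 0.09 × 738 = 66. Only some of these would be significant.

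**What the fix could cost the equivalence analysis**

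SAP 3.4 removes from PP a subject who took fewer than 5 doses (item 4). mITT needs only one dose, so its membership does not change.

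Inputs: 246 per arm and a 12.4% mITT loss (Protocol 9.1) give 246 × 0.876 = 215. Cure rates are 36% and, at the planned maximum gap of 4 points, 40%. From SAP 3.7.1:

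- se = √[(0.40 × 0.60 + 0.36 × 0.64)/n]
- half-width h = 1.645 × se + 1/n, since (1/n + 1/n)/2 = 1/n
- power ≈ Φ[(0.20 − h − 0.04)/se] − Φ[(−0.20 + h − 0.04)/se]

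At n = 215: se = 0.0468, h = 0.0816, power = Φ(1.676) − Φ(−3.387) = 95.3%.

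| PP before the fix | Further loss per arm | n per arm | h | Power |
|---|---|---|---|---|
| Equal to mITT (best case) | 0 | 215 | 0.0816 | 95.3% |
| Equal to mITT | 3 (6 in total, the proxy's upper limit rounded up) | 212 | 0.0822 | 95.0% |
| Equal to mITT | 22 (9% of 246) | 193 | 0.0864 | 93.1% |
| 15% of mITT already lost (assumed) | 0 | 183 | 0.0889 | 91.8% |
| 15% already lost | 3 | 180 | 0.0896 | 91.4% |
| 15% already lost | 22 | 161 | 0.0951 | 88.1% |

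Exact binomial enumeration of the same rule gives 95.4%, 95.2% and 93.2% for the first three rows.

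**The case against.** The best case for leaving the sheet alone is that the contact route is already there. The note's first sentence allows the study doctor to direct otherwise, and the irritation bullet sends the woman to that same person, who can stop treatment and has the label. Appendix 2 is an adapted trial handout and was never meant to copy the label: it also drops the twice-daily directions and adds trial rules. A reason for contact-first can be guessed from SAP 3.4, since early stopping removes a subject from the equivalence population. The proxy case stopped for mild burning, so it measures neither significant irritation nor the effect of this wording.

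Much of this stands. It makes the sheet a contact-first instruction with a small consequence, and it shows that the frequency is poorly known. It does not restore the label's permission to stop before reaching anyone. The missed-dose bullet does not fill that gap, because it tells the subject to resume the next evening.

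Two stronger readings are tempting. A reader might infer that subjects hold two contradictory instructions, but nothing shows that they receive the label's patient directions. A reader might also infer that Protocol 13 is breached. That clause binds investigators to the protocol and the label together, Appendix 2 is part of the protocol, and a consulted investigator can still apply the label's advice. The clause makes the unexplained difference worth correcting; it does not prove a violation.

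**Conclusion.** The point holds as a minor safety-wording improvement. The textual difference is certain. Its consequence is small: about one nightly dose per day of delay, for roughly 1 active-arm woman on the 1/505 proxy (0.02 to 5.4). That estimate assumes stopping for burning in the label's trial stands in for significant irritation here.

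The documents do not support an inference of bias between arms or of an effect on type I error. What the consent form says about stopping cannot be judged, because consent pages are not in the reviewed files, so no gap there is claimed.

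On power, the proxy-based loss is negligible whether PP equals mITT (95.3% to 95.0%) or 15% has already been lost (91.8% to 91.4%). It would be wrong to add that power stays above 90% whatever happens. If 9% of each randomised active arm left PP on top of an assumed 15% mITT-to-PP loss, power would be 88.1%. That scenario is extreme, since it treats every irritative symptom as a reason to stop, and the documents give no PP attrition figure.

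**What to change.** Make two edits to Appendix 2. In the irritation bullet, put the label's instruction to discontinue use back in front of the referral to the study doctor. In the note, open the sentence against stopping with an exception for significant irritation that points to that bullet. Every other reason for stopping would still go through staff first.

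The cost is two sentences in one handout and an IRB submission. A few subjects may take fewer than five doses and leave PP. On the proxy this is about one active-arm subject, and no change to sample size or analysis is needed.
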